9.4. Randomization and Blinding

This study will be conducted in a double-blind, placebo-controlled manner. Allocation to one of two treatment groups (OCA or placebo) will occur on a 1:1 ratio across sites and will be stratified by UDCA treatment (yes/no) and mean baseline bilirubin categories ($>ULN/\leq ULN$), as specified by the central laboratory. The randomization will be based on a predefined randomization code (generated by the Sponsor or designee) using an interactive web response system (IWRS), which the Sponsor intends will serve as a computer-based subject registration system at Screening and Day 0. The IWRS will also serve as an investigational product inventory and management system and may be integrated with the study database.

The Investigator or designee will be required to register the subject in the IWRS and may be prompted to provide subject data necessary to properly randomize and allocate the subject to treatment. A randomization number will be assigned (refer to [Section 9.5.2](#) below) and investigational product dispensing information (ie, bottle number[s]) will be provided.

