13.1.2. Determination of Sample Size

The target population is subjects who are at higher risk of liver-related clinical complications. Eligible subjects will have a diagnosis of PBC with bilirubin levels $>ULN$ and $\leq 5x ULN$ and/or $ALP > 3 \times ULN$. The following assumptions were used in sample size calculations:

- Exponential survival curves, placebo survival estimate of 0.6 at 8 years with a hazard ratio of 0.60, and total study duration of 10 years (from first subject enrolled), allowing for 4 years of subject accrual and 6 years of follow up.
- Subjects will be randomized in a 1:1 ratio to placebo or OCA.
- The 2 groups will be compared using a 2-sided log rank test at the 5% level of significance.
- Two interim analyses and one final analysis are planned. The first interim analysis will be performed when 50% of the target events are accrued and the second interim will be performed when 75% of the target events are accrued.
- A dropout rate of 10% is assumed

Based on the randomization ratio, significance level, and assumed hazard ratio, a total of 127 events (both groups combined) will provide 80% power to demonstrate a statistically significant difference between OCA and placebo on time to liver-related outcomes, including all-cause mortality.

In addition, based on the remaining assumptions stated above, it is estimated that approximately 428 subjects will be enrolled to attain 127 events.

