Analyses of changes in MELD score, Child-Pugh score, MRS, IgM, CRP, TNF- α , FGF-19, CK-18, C4, and ELF score will be summarized and analyzed using the Wilcoxon Rank Sum Test to compare treatment groups. The median differences and 95% CI of the median differences between treatment groups will be constructed using Hodges-Lehmann estimate. If the median differences between treatments are not symmetrical around the median, the Sign Test may be used.

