13.1.10. Multiple Comparisons/Multiplicity

The key secondary efficacy endpoints are as follows:

- Time to MELD score ≥ 15
- Time to first occurrence of liver transplant or death (all-cause)
- Change from Baseline in total bilirubin at end of study
- Change from Baseline in ALP at end of study

The hypothesis testing of key secondary analyses will compare placebo and OCA and will be conducted in a sequential closed testing gate-keeping procedure (in the order in which the key secondary endpoints are stated above), provided that the primary efficacy endpoint comparison is statistically significant in favor of OCA. If the primary comparison is not statistically significant then comparison of the secondary endpoints will be considered as descriptive and exploratory.

This procedure controls the study-wise type I error.

- First (step 1) placebo and OCA will be compared with respect to the primary efficacy endpoint. If the comparison achieves statistical significance at 2-sided 0.05 level in favor of OCA group, then
- The time to MELD score ≥ 15 will be compared between placebo and OCA (step 2). If the comparison achieves statistical significance at 2-sided 0.05 level in favor of OCA group, then
- The time to liver transplant or death (all-cause) will be compared between placebo and OCA (step 3). If the comparison achieves statistical significance at 2-sided 0.05 level in favor of OCA group, then
- Change from Baseline in total bilirubin will be compared between placebo and OCA (step 4). If the comparison achieves statistical significance at 2-sided 0.05 level in favor of OCA group, then
- Change from Baseline in ALP at the end of study will be compared between placebo and OCA (step 5).

If at any step defined above the comparison is not statistically significant at the 2-sided 0.05 level then the remaining comparisons in the stated hierarchy will be considered descriptive and exploratory. The study-wise type I error will be maintained with the above closed procedure.

Additional efficacy endpoints will be analyzed; however, hypothesis tests will be applied for descriptive and exploratory purposes only.

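### The Sign Test is offered as a fallback for comparing OCA with placebo on ten exploratory markers, but it is not defined for two independent arms

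*Protocol*

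**What the plan says.** The last paragraph of Protocol section 13.1.5 covers changes in MELD score, Child-Pugh score, Mayo Risk Score, IgM, CRP, TNF-α, FGF-19, CK-18, C4 and ELF score. These "will be summarized and analyzed using the Wilcoxon Rank Sum Test to compare treatment groups". The estimate follows: "The median differences and 95% CI of the median differences between treatment groups will be constructed using Hodges-Lehmann estimate". The paragraph closes with the fallback: "If the median differences between treatments are not symmetrical around the median, the Sign Test may be used".

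On the design, section 9.4 states: "Allocation to one of two treatment groups (OCA or placebo) will occur on a 1:1 ratio across sites". Section 13.1.2 repeats it: "Subjects will be randomized in a 1:1 ratio to placebo or OCA".

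On the standing of these endpoints, section 13.1.10 sets out a hierarchy of the primary endpoint and four key secondary endpoints. It then says: "Additional efficacy endpoints will be analyzed; however, hypothesis tests will be applied for descriptive and exploratory purposes only". None of the ten markers is in that hierarchy. MELD appears there only as time to a score of 15 or more, which is a separate, time-to-event analysis.

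**The concern.** All three sentences concern the contrast between treatment groups, so the Sign Test is offered as another way to test that contrast. It counts positive and negative signs among differences that belong together: a subject's change from baseline, or the difference within a matched pair. Two parallel arms supply no such differences between OCA and placebo.

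The condition for switching does not fit either. Checking differences for symmetry, and falling back on the sign test when it fails, is the usual rule for one-sample or paired data analysed with the signed-rank test. It seems to have been carried into a two-sample analysis.

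At stake is whether a p-value reported for these markers would address OCA versus placebo. Markers of inflammation and fibrosis serve a stated secondary objective (section 6.2), so the answer matters for interpretation even though nothing confirmatory rests on it.

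**Working it through.** No sample size, event count, power or alpha in the protocol depends on this sentence, so there is no figure to reproduce. The check is by logic, with a short simulation as illustration.

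**Inputs from the protocol**
- Two independent arms, 1:1 (sections 9.4 and 13.1.2).
- Planned enrolment: "it is estimated that approximately 428 subjects will be enrolled to attain 127 events" (section 13.1.2). Per arm: 428 / 2 = 214.
- Main test, estimator and fallback as in section 13.1.5.

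**Assumed for illustration:** the distributions of change, which the protocol does not give. Skewed ones were chosen because asymmetry is the stated trigger.

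**Step 1: is there any pairing?** Matching appears in the protocol only for historical controls (sections 13.1.1.1 and 13.1.8), where the listed outcomes are death and liver transplant. Nothing pairs an OCA subject with a placebo subject for the ten markers.

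**Step 2: does the rank-sum test need symmetry?** No. Let X be the change for an OCA subject and Y that for an independent placebo subject. If the treatment has no effect, X and Y have the same distribution, so X − Y and Y − X do too, and X − Y is symmetric about 0 however skewed the marker is. Under a pure shift Δ, X − Y is symmetric about Δ. Asymmetric between-arm differences can therefore arise only when the arms differ in shape. That limits the reading of the Hodges-Lehmann estimate as a simple shift, but it does not create pairs for a sign test.

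As a numerical check, both arms were drawn from the same heavily skewed lognormal distribution (log-scale SD 1.5), 4,000 runs, 214 per arm. The rank-sum test rejected in 4.4% of runs at nominal 5%. The simulation standard error is √(0.05 × 0.95 / 4000) = 0.34 percentage points, so this is consistent with the nominal level.

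**Step 3: what could a sign test be computed on?** There are two possibilities.

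*(a) OCA–placebo pairs formed arbitrarily.* One fixed data set was generated: change = exponential(1) − 0.5 in one arm and exponential(1) − 0.25 in the other, 214 each. It was re-paired at random 2,000 times.

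| Test on the same data | p-value |
|---|---|
| Sign test, range over pairings | 6.6 × 10⁻¹⁰ to 0.024 |
| Rank-sum test | 7.2 × 10⁻⁷ (single value) |

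The sign-test result depends on a pairing that carries no information.

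*(b) Change from baseline within an arm.* Both arms were drawn from exponential(1) − 0.5, so there is no treatment difference, but both have moved from baseline: P(change > 0) = exp(−0.5) = 0.607. Over 2,000 runs:

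| Test | Rejected at 5% |
|---|---|
| Within-arm sign test | 87.7% |
| Rank-sum test between arms | 4.9% |

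The within-arm test correctly detects movement from baseline. It simply does not address OCA versus placebo.

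The percentages and p-values depend on the assumed distributions. The logical conclusion does not: neither construction is a test of the treatment contrast.

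**The case against.** Four points can fairly be made on the other side.

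**The wording is permissive.** The rank-sum test is what will be done; the Sign Test is only something that may be used. A reader might infer that the plan replaces a valid test with an invalid one. The text does not support that: nothing withdraws the rank-sum result or the Hodges-Lehmann interval, and exposure exists only if asymmetry is declared and the option is taken. The documents give no basis for saying how often that would happen. This stands and limits the point.

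**The endpoints are exploratory.** This also stands. Section 13.1.10 settles it, and no confirmatory conclusion is touched.

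**The SAP may settle the matter.** Section 13 leaves details of analyses and tests to an SAP approved before the first interim analysis and unblinding. A reader might infer that the choice of test would be made after seeing unblinded results; that is not established. But the point is not that detail is missing. The protocol names an unsuitable test, and an SAP that quietly omits it would depart from the protocol.

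**The sentence may have meant a within-arm test.** It speaks of differences between treatments and follows a between-group estimate, so that reading does not fit. For the same reason, one should not assert that the reported p-value would test within-arm change. That is one guess at how an undefined instruction might be carried out.

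**Conclusion.** The point holds as a minor error in the stated analysis rule. For independent arms the Sign Test is undefined as a test of OCA against placebo, and its symmetry trigger gives no reason to leave the rank-sum test.

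Its reach is ten exploratory markers, and only where the option is exercised. The primary endpoint, the four key secondary endpoints, the type I error control and the sample size are unaffected. The 87.7% rejection rate should not be read as the false-positive rate of the planned analysis: it comes from assumed distributions and from a within-arm reading that the wording does not support. It shows only that the two tests answer different questions.

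The conclusion rests on the arms being unpaired for these markers, which is what the protocol describes. It does not depend on any assumed distribution.

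**What to change.** Delete the Sign Test sentence from section 13.1.5 and keep the Wilcoxon rank-sum test with the Hodges-Lehmann estimate and its interval, whatever the shape of the data. If a fallback is wanted, name a valid two-sample method instead, such as a two-sample median test or a bootstrap interval for the difference in medians.

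Optionally, use a van Elteren test stratified by the randomization factors (UDCA use and baseline bilirubin category), in line with the stratified analyses elsewhere in section 13. That is a preference; the unstratified rank-sum test is acceptable for exploratory markers.

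The cost is one sentence, with no effect on data collection, sample size or alpha. Because a protocol change needs an amendment and ethics review (sections 16.1 and 17.2), the practical route is to state in the SAP now that the option will not be used, and to remove the sentence at the next amendment made for other reasons.

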13.1.5.1. Association of Biochemistry with Clinical Outcomes and Clinical Benefit

The association between biochemistry including ALP and bilirubin with clinical outcomes will be assessed and the clinical benefit of OCA using biochemistry as a surrogate endpoint will be evaluated. Detailed analysis will be described in the SAP.

Based on the association between biochemical changes and clinical outcomes described above, clinical benefit of OCA using biochemistry as a surrogate endpoint for key subpopulations of interest will be evaluated. This analysis will be further described in the SAP.

13.1.6. Exploratory Efficacy Analyses

13.1.6.1. Responder Analyses

The percentage of subjects with a decrease in ALP of $\geq 15\%$ and $\geq 40\%$ from Baseline will be summarized by treatment group. In addition, the percentage of subjects with ALP \leq ULN will be summarized by treatment group.

The percentage of subjects that meet the criteria of a responder based on each of the definitions below will be summarized by treatment group. The response classification at baseline will also be included in the summary:

- ALP $\leq 3x$ ULN and AST $\leq 2x$ ULN and total bilirubin \leq ULN ([Corpechot 2008](#))
- ALP $\leq 1.5x$ ULN and AST $\leq 1.5x$ ULN and total bilirubin \leq ULN ([Corpechot 2011](#))
- ALP $\leq 1.67x$ ULN and total bilirubin \leq ULN ([Momah 2012](#))
- Normal bilirubin (values \leq ULN) and normal albumin (values \geq lower limit of normal) ([Kuiper 2009](#))
- ALP $\leq 1.76x$ ULN ([Kumagi 2010](#))

Responder analyses will compare treatment groups using a Cochran–Mantel–Haenszel test stratified by the randomization stratification factor. Missing values will be considered as a non-responder.

13.1.7. Pharmacoeconomic and Health Outcomes Endpoints

Sufficient data will be collected on resource utilization and quality of life to undertake cost-effectiveness analyses that are relevant to the major countries taking part in this study. Resource utilization data on hospitalizations, healthcare provider visits, and medications will be combined with appropriate national unit costs to calculate a cost per patient per year in the study.

Quality of life data from patient-reported outcomes measures will be combined with survival data to calculate quality adjusted time in the study per patient. Cost-effectiveness analyses will report the incremental cost per major clinical outcome averted, liver-related death averted, life-year gained and quality-adjusted life year gained, including OCA as part of usual care versus usual care without OCA. Analyses will be conducted within the study and using a lifetime perspective. A separate economic analysis plan will be prepared and reported separately from this protocol.

13.1.8. Supportive Analysis

Per the International Conference on Harmonisation (ICH) E10 guidance, “where no obvious single optimal external control exists, it may be advisable to study multiple external controls”. In order to address the risks associated with the inclusion of a long-term placebo arm, supportive analyses of the primary endpoint will compare clinical outcomes in the OCA treatment arm to historical controls, which serves as an external control for supportive analysis.

In an attempt to avoid the inherent biases with historical controls and to maintain the integrity of this comparison, one can invoke matching methods to optimize comparability and find a historical control that is “similar” to a participating subject. The historical database control should be as similar as possible to the study population and should have been exposed to a similar standard of care (see [Section 5.5.2.3](#)).

A propensity score can be used to reduce bias through matching, stratification, regression adjustment, or some combination. Propensity scores use information from a pool of patients who do not participate in the study (historical controls) to identify what would have happened to participating subjects in the absence of the treatment. By comparing how outcomes differ for treated subjects relative to historical controls, it is possible to estimate the effects of the treatment between the treated subjects and the matched natural history subjects.

A full range of covariates across which the treatment and historical controls might differ will be considered to mitigate potential bias. Although the results of using matching controls are conditional only on the observed covariates, if one has the ability to measure many of the covariates that are believed to be related to the treatment assignment, then one can be fairly confident that approximately unbiased estimates for the treatment effect can be obtained. Both UK-PBC Group and the Global PBC Study Group formally collect numerous covariates that could be used for propensity score estimation including standard of care, eg, UDCA.

Historical controls will be chosen based on the same inclusion/exclusion criteria where possible. Propensity scores will be estimated using the available covariates that predict receiving the treatment. Only covariates and not outcome variables will be included in the propensity score estimation, to avoid biased results that are in favor of one treatment.

The covariates and factors collected in the historical databases will be specified in the SAP.

Propensity scores will be estimated first through a logistic regression model with treatment group as the dependent variable and the above covariates/factors as independent variables. Then the stratum boundaries are determined based on the propensity score values for both groups (OCA population and control [historical and randomized placebo]) combined or in the OCA population or historical control group alone. Based on recommendations in the literature, quintiles of the estimated propensity score from the combined group will be used to determine the stratum boundary cut-offs for the different strata.

The baseline characteristics between treated and natural history subjects in the matched dataset will be summarized and presented in a tabular format. Statistical methods such as Wilcoxon Rank-Sum test will be used to assess the balance for baseline covariates. The standardized difference and variance ratios for these covariates will also be calculated. In addition, box plots of propensity scores for treated and natural history subjects will be separately presented, to further assess the adequacy of matching.

A third-party statistician(s) will perform the propensity score modeling and matching. This third-party statistician(s) will be separate and independent from the statistician(s) who will assess the success of matching and perform efficacy analyses. Outcome events collected in the historical database are: death (liver-related and all-cause), liver transplant, HCC, and other. Other is defined as cirrhosis or decompensation such as ascites, variceal bleed, and encephalopathy.

The propensity score quintile will be then be used as the stratification factor in the stratified log rank test to compare randomized OCA-treated subjects in the ITT population and historical controls (Overall Historical Control Population: both the UK-PBC Group and Global PBC Study Group databases) on the following outcomes:

- Time to death (all-cause)
- Time to liver-related death
- Time to liver transplant
- Time to liver transplant or death (all-cause)
- Time to liver transplant or liver-related death

KM estimates of the distribution of the time-to-event will be tabulated and graphed by treatment group. The tabulation will include the KM estimate of the medians and corresponding 95% CIs if the medians can be estimated. The number and percent of subjects censored and with events will be presented. The hazard ratio and 95% CI will be determined based on a Cox regression model stratified by randomization strata to estimate the magnitude of the effect.

Sensitivity analyses will be conducted limiting to the separate individual historical control databases, ie, UK-PBC Group and Global PBC Study Group. To evaluate the robustness of the propensity score estimations, additional algorithms and factors may be considered.

Although the study is designed as a placebo-controlled study, the DMC may recommend changes to study conduct based on the pre-specified interim analyses (see [Section 13.1.12](#)), including the potential use of a revised primary efficacy analysis. This analysis would compare all subjects in the OCA population, to all control subjects (randomized placebo and historical controls) on time to liver transplant or death (all-cause), using similar statistical methodology as specified above.

Notably, the planned primary analysis would not be revised without prior agreement with regulatory authorities.

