1. Definite or probable PBC diagnosis (consistent with American Association for the Study of Liver Diseases [AASLD] and the European Association for the Study of the Liver [EASL] practice guidelines; [Lindor 2009](#); [EASL 2009](#)), as demonstrated by the presence of ≥2 of the following 3 diagnostic factors:
 - History of elevated ALP levels for at least 6 months
 - Positive antimitochondrial antibody (AMA) titer or if AMA negative or in low titer (<1:80) PBC-specific antibodies (anti-GP210 and/or anti-SP100 and/or antibodies against the major M2 components [PDC-E2, 2-oxo-glutaric acid dehydrogenase complex])
 - Liver biopsy consistent with PBC
2. A mean total bilirubin >ULN and ≤5x ULN and/or a mean ALP >3x ULN
3. Age ≥18 years
4. Either is not taking UDCA (no UDCA dose in the past ≥3 months) or has been taking UDCA for at least 12 months with a stable dose for ≥3 months prior to Day 0
5. Contraception: Female subjects must be postmenopausal, surgically sterile, or, if premenopausal (and not surgically sterile), be prepared to use ≥1 highly effective method of contraception during the study

and for 30 days after the end of treatment. Highly effective methods of contraception per the CTFG guidelines are those that alone or in combination results in a failure rate of less than 1% per year when used consistently and correctly. Highly effective methods of contraception are as follows:

- Intrauterine device
 - Intrauterine device (IUD)
 - Intrauterine hormone-releasing system (IUS)
- Bilateral tubal occlusion
- Vasectomy (partner)
- Combined (estrogen and progestogen containing) hormonal contraception (eg, oral, intravaginal or transdermal) associated with inhibition of ovulation. If oral contraceptives are used, they must be used in combination with a male or female condom. Female subjects should have been on the hormone contraception for at least 8 days prior to Day 1.
- Progestogen-only hormonal contraception (eg oral, injectable or implantable) associated with inhibition of ovulation. If oral contraceptives are used, they must be used in combination with a male or female condom. Female subjects should have been on the hormone contraception for at least 8 days prior to Day 1.
- Sexual abstinence, if in line with the preferred and usual lifestyle of the subject (where abstinence is defined as refraining from heterosexual intercourse during the entire period of risk associated with study treatments).

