5.5.2.3. Rationale for Control Groups

Placebo Control Group

The use of a randomized placebo control group added to established standard of care provides the best scientific evidence of efficacy and safety. The use of a placebo control provides a concurrent comparator group, accounting for not only a placebo effect but a standard of care effect. Notably, accounting for the standard of care effect is critical when designing an outcome-based study conducted globally when there are regional differences in the treatment of subjects with PBC.

Historical Control Group

The available robust historical PBC observational datasets (UK-PBC and Global PBC Study Group) will also be leveraged to provide further comparative evaluation of the clinical benefit of OCA. Each database includes >6000 patients with long-term follow-up.

Comparison of OCA treatment to the historical controls may provide utility in addressing potential bias or confounds associated with the placebo arm. For example, bias associated with the potential addition of commercial OCA and/or differences in long-term standard of care between the treatment arms including ancillary treatments and diagnostics.

Therefore, further evaluation of the effect of OCA will compare OCA treatment versus historical controls, and will be supportive to placebo comparisons (ie, comparisons to historical and placebo controls will be evaluated separately).

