8.3. Subject Exclusion Criteria

1. History or presence of other concomitant liver diseases including:
 - Hepatitis C virus infection
 - Active hepatitis B infection; however, subjects who have seroconverted (hepatitis B surface antigen and hepatitis B e-antigen negative) may be included in this study after consultation with the Medical Monitor.
 - Primary sclerosing cholangitis
 - Alcoholic liver disease
 - Definite autoimmune liver disease or overlap hepatitis
 - Nonalcoholic steatohepatitis
 - Gilbert's Syndrome
2. Presence of clinical complications of PBC or clinically significant hepatic decompensation, including:

- History of liver transplant, current placement on a liver transplant list, or current MELD score >12. Subjects who are placed on a transplant list despite a relatively early disease stage (for example per regional guidelines) may be eligible as long as they do not meet any of the other exclusion criteria.
 - Cirrhosis with complications, including history (within the past 12 months) or presence of:
 - Variceal bleed
 - Uncontrolled ascites
 - Encephalopathy
 - Spontaneous bacterial peritonitis
 - Known or suspected hepatocellular carcinoma
 - Prior transjugular intrahepatic portosystemic shunt procedure
 - Hepatorenal syndrome (type I or II) or Screening (visit 1 or 2) serum creatinine >2 mg/dL (178 µmol/L)
3. Mean total bilirubin >5x ULN
 4. Subjects who have undergone gastric bypass procedures (gastric lap band is acceptable) or ileal resection or plan to undergo either of these procedures.
 5. Other medical conditions that may diminish life expectancy, including known cancers (except carcinomas *in situ* or other stable, relatively benign conditions).
 6. If female: plans to become pregnant, known pregnancy or a positive urine pregnancy test (confirmed by a positive serum pregnancy test by the central laboratory), or lactating.
 7. Known history of human immunodeficiency virus infection.
 8. Medical conditions that may cause non-hepatic increases in ALP (eg, Paget's disease or fractures within 3 months).
 9. Other clinically significant medical conditions that are not well controlled or for which medication needs are anticipated to change during the study.
 10. History of alcohol abuse or other substance abuse within 1 year prior to Day 0.

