13.1.1.1. Comparability of Historical Controls

Utilization of both historical control/observational databases (UK-PBC and Global PBC Study Group), with more than 6000 subjects each, allow for a rigorous subject level meta-analysis. The historical databases include long-term follow up, detailed subject-level information such as baseline clinical characteristics, longitudinal liver biochemistry, and long-term outcomes, and span a broad range of subject characteristics that may influence disease (disease state, age, gender, and regional differences in standard of care). Historical controls from both databases will be chosen based on the same study inclusion/exclusion criteria. Propensity score matching method will be utilized to select historical controls that match the treated subjects using available covariates. The adequacy of matching will be assessed by statistical methods described under [Section 13.1.8](#).

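### Sections 13.1.1.1 and 13.1.8 give different eligibility rules for historical controls; the looser one can admit ineligible controls that propensity methods cannot correct for, probably in OCA's favour

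*Protocol*

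**What the plan says.** Two sections of the current protocol set the rule for choosing historical controls.

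- Section 13.1.1.1: "Historical controls from both databases will be chosen based on the same study inclusion/exclusion criteria". There is no condition.
- Section 13.1.8, which specifies the analysis: "Historical controls will be chosen based on the same inclusion/exclusion criteria where possible".

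Section 13.1.8 then describes the adjustment: "Propensity scores will be estimated using the available covariates that predict receiving the treatment". It concedes the limit of the method: "Although the results of using matching controls are conditional only on the observed covariates". Its balance checks are a rank-sum test, standardized differences, variance ratios and box plots of the score. The outcomes compared are all-cause death, liver-related death, transplant, and combinations of death with transplant.

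Section 13.1.1 adds a condition: each historical control population must have been shown comparable to the randomized subjects in characteristics and in disease progression. Section 5.5.2.3 calls the comparison supportive and says "comparisons to historical and placebo controls will be evaluated separately".

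**The concern.** An analyst cannot follow both rules. Under 13.1.8, if a database does not record a criterion, that criterion was enforced on every OCA subject and is not enforced on the controls. The protocol does not say which criteria are affected or what happens to a patient whose status on one is unknown.

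The criteria are not neutral for prognosis. Section 8.3 excludes "History of liver transplant, current placement on a liver transplant list, or current MELD score >12", decompensation within the past 12 months, hepatocellular carcinoma, raised creatinine, and "Other medical conditions that may diminish life expectancy, including known cancers". Patients of this kind left among the controls would tend to die or be transplanted sooner, which makes OCA look better than it is.

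The comparison carries weight. Section 5.5.2.3 offers it as a way to address bias in the placebo arm, for example from commercial OCA. Section 13.1.8 also allows, with prior regulatory agreement, a revised primary analysis that pools historical controls with placebo on time to transplant or death.

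**Working it through.** **The two rules.** Both sentences are current text. The change summaries for Version 4 (Appendices H and I) show that the words *where possible* were struck from 13.1.1.1; they remain in 13.1.8. The summaries are context only: the conflict is between two live sections. Section 13.1.8 leaves the list of covariates to the SAP, but the protocol fixes the eligibility rule itself, twice and differently.

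**What adjustment can reach.** The score uses recorded covariates and the balance checks examine recorded covariates. An unrecorded criterion therefore escapes selection, adjustment and checking, except as far as it correlates with something recorded.

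**The plan's own figures.** Section 13.1.2 sizes only the randomized comparison; it gives no figure for the historical one.
- Placebo hazard: −ln(0.6)/8 = 0.0639 per year. OCA hazard: 0.60 × 0.0639 = 0.0383.
- With 4 years of accrual and 6 of follow-up, P(λ) = 1 − (e^(−6λ) − e^(−10λ))/(4λ). This gives 0.398 and 0.263, mean 0.331.
- 127/0.331 = 384, and 384/0.9 = 427, against 428 stated. The design figure reproduces and is not touched by this point.

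**Illustration of size.** Assumptions, none of them in the protocol: OCA inactive; 20% 8-year risk of death or transplant in eligible patients; two controls per OCA subject; controls followed as in the trial; a share f of controls ineligible, with k times the hazard; no propensity adjustment. OCA subjects: 428/2 × 0.9 = 193 (rounded); controls: 386.
- Eligible hazard: λ = −ln(0.8)/8 = 0.0279. P(λ) = 0.200; mean time at risk P/λ = 7.16 years. Expected OCA events: 193 × 0.1996 = 38.5.
- f = 10%, k = 3: the ineligible have P = 0.486 and 5.80 years. Controls overall: P = 0.9 × 0.1996 + 0.1 × 0.486 = 0.228; time 0.9 × 7.16 + 0.1 × 5.80 = 7.02 years. The rate is 0.0325, a ratio b = 1.165 to the eligible hazard (apparent HR 0.86). Control events: 88.1.
- f = 10%, k = 5: the ineligible have P = 0.668 and 4.79 years. Controls overall: P = 0.246, time 6.92 years, b = 1.277 (apparent HR 0.78). Control events: 95.1.
- Chance of a false significant benefit: Φ(−1.96 + ln b / √(1/d_OCA + 1/d_control)).
  - k = 3: Φ(−1.96 + 0.153/0.193) = 12%.
  - k = 5: Φ(−1.96 + 0.244/0.191) = 25%.
- A simulated log-rank test on the same inputs gives 11.6% and 23.9%.

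The simpler formula b = 1 + f(k − 1) gives 1.20 and 1.40, with false-benefit chances of 16% and 43%. It holds only at time zero: high-risk controls have their events early and leave the risk set, so it overstates the effect over 6 to 10 years.

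**Opposite direction.** If the ineligible controls have half the hazard, the same calculation gives an apparent HR of 1.06 at f = 10% and 1.18 at f = 30%, against OCA.

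**The case against.** The strongest reply is that 13.1.8 carries a leftover phrase. The sponsor removed it from 13.1.1.1, so the unconditional rule is the intended one, and Section 13.1.1 separately requires demonstrated comparability. That is a fair reading of intent, but the section that runs the analysis still says otherwise. Section 13.1.8 also names no method for showing comparable disease progression; its checks are on baseline covariates and the score.

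Three stronger readings are tempting, and the document does not support them.

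- *That the listed exclusions are in fact unrecorded.* No section says so. Section 13.1.1.1 says the databases hold baseline clinical characteristics and longitudinal biochemistry, and 13.1.8 lists transplant, hepatocellular carcinoma and decompensation among the outcome events they collect. Several exclusions may well be checkable.
- *That the bias must favour OCA.* Failing the entry criterion "A mean total bilirubin >ULN and ≤5x ULN and/or a mean ALP >3x ULN" on its lower limits would admit lower-risk patients. That criterion can probably be applied from the recorded biochemistry, so the direction is likely, not certain.
- *That OCA versus historical controls should count only if placebo versus historical controls gives a hazard ratio near 1.* Section 5.5.2.3 wants the historical comparison partly because placebo subjects may move to commercial OCA. If they do and it works, that ratio departs from 1 exactly where the comparison is meant to help. Keeping the two comparisons separate is not an error.

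**Conclusion.** The contradiction is real and should be resolved. Its consequence is a possible bias in a supportive comparison, probably in OCA's favour, that the planned propensity methods cannot remove for unrecorded criteria.

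The size cannot be derived from the protocol. Under the assumptions above, the control hazard is about 16% higher at 3 times the hazard and about 27 to 28% higher at 5 times. The chance of a false significant benefit is about 11 to 12% and 24 to 25%, against 2.5%. Recorded covariates that correlate with a missing criterion would reduce these figures.

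A reader might infer that the trial's main result is at risk. It is not: the randomized primary test and its type I error are unaffected unless the revised primary analysis in 13.1.8 is adopted.

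**What to change.** 1. Delete *where possible* from Section 13.1.8 so that it matches 13.1.1.1.
2. Exclude from the main historical comparison any control whose key prognostic eligibility cannot be verified at the index date: bilirubin and ALP limits, MELD, transplant or listing, recent decompensation, hepatocellular carcinoma and creatinine. Add a sensitivity analysis that includes these controls.
3. Name as a limitation any criterion that neither database can verify.
4. As a diagnostic of the comparability that Section 13.1.1 requires, run the same propensity-stratified comparison of randomized placebo against historical controls, with and without censoring at commercial OCA. Report it beside the OCA-versus-historical result, with no pass/fail threshold. Censoring at commercial OCA may be informative, which is why both versions are needed.

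The cost is a change of wording, a smaller control pool and one extra run of the analysis. With more than 6000 patients in each database before selection, there should be room for the loss.
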